3.3. Level of Significance

The level of significance for the primary endpoint in Phase 2 is 1-sided 5%, which is deemed acceptable for a proof-of-concept study.

3.4. Sample Size Considerations

3.4.1. Sample Size for the Phase 1 Portion of the Study

The primary objective of the open-label Phase 1 portion of the study is to determine the MTD and DLT of epacadostat in combination with pembrolizumab. The total number of subjects will depend on the number of dose levels tested before the MTD is established. Approximately 54 subjects (3-9 subjects per dose level for 4 dose levels plus an additional 9 subjects treated at 50 mg BID, 100 mg BID and potentially at 300 mg BID) will be included based on the dose escalation. Dose escalation will follow a 3 + 3 + 3 design algorithm, as defined in Section 3.1. Based on this algorithm, 3 evaluable subjects are enrolled in each cohort with a maximum of 9 subjects at any dose level (except for MTD or PAD, where a total of 9 subjects will be treated to further evaluate safety and confirm it as the RP2D).

3.4.2. Sample Size for the Phase 2 Expansion Portion of the Study

The sample size of 18 to 42 subjects is expected to be enrolled in each of the 14 response expansion cohorts (ie, NSCLC PD-L1 high, NSCLC PD-L1 low/negative or indeterminate, melanoma, transitional cell carcinoma of the GU tract, TNBC, ovarian cancer, SCCHN, DLBCL, RCC, MSI-high CRC, gastric cancer, HCC). The sample size for each independent cohort yields a power of 80% to detect an increase in ORR by about 20% (Ha) from historical response rate (H0). This assumes a 1-sided alpha of 5% and 10% lost to follow-up. See details in Table 4.

A Simon 2-stage design will be used for the primary refractory and relapsed melanoma cohorts. In the first stage for the primary refractory cohort, 8 subjects will be enrolled. If at least 1 response is observed in those 8 subjects, an additional 19 subjects will be enrolled, for a total sample size of 27 subjects. The power for this design is 80% and the Type I error is 3.2%.

In the first stage for the relapsed melanoma cohort, 11 subjects will be enrolled. If at least 2 responses are observed in those 11 subjects, an additional 7 subjects will be enrolled, for a total sample size of 18 subjects. The power for this design is 80% and the Type I error is 2.7%.

	ORR		
Tumor Type	HO	На	Sample Size
NSCLC high positive (PD-L1 TPS \geq 50%)	36%	56%	42
NSCLC low/negative or indeterminate (PD-L1 TPS < 50% or indeterminate)	12%	32%	25
Melanoma (immune checkpoint-naive)	32%	52%	40
Transitional cell carcinoma of the GU tract	24%	44%	36
TNBC	19%	39%	32
Ovarian cancer	20%	40%	33
SCCHN	19%	39%	32
DLBCL	36%	57%	37
RCC	25%	45%	36
MSI-high CRC	57%	80%	29
Gastric cancer	14%	34%	27
НСС	19%	39%	32
Melanoma (primary refractory)	3%	20%	27 ^a
Melanoma (relapsed)	10%	35%	18 ^a
Total			446

Table 4:Sample Size Calculation for Each Cohort: Comparing With a Known
Proportion

^a Maximum possible sample size for Simon 2-stage design. Actual sample size may be less.

3.5. Schedule of Assessments

All study assessments will be performed as indicated in the schedules of assessments for the Q3W schedule (refer to Tables 12 and 13 in Protocol Amendment 10). The order of assessments is suggested by the order of mention within the schedules.

4. DATA HANDLING DEFINITIONS AND CONVENTIONS

4.1. Scheduled Study Evaluations and Study Periods

4.1.1. Day 1

Day 1 is the date of first dose of epacadostat or pembrolizumab.

4.1.2. Study Day

The study day at a visit or reporting date will be calculated by the visit or reporting date minus the Day 1 date plus 1 (visit date – Day 1 date + 1). This study day will be subtracted by 1 if it is ≤ 0 , so that a study day of 0 will never occur. A study day of -1 indicates 1 day before Day 1.

4.1.3. Scheduled Visits

Study evaluations in weeks or days from Day 1 are presented in the Schedule of Assessments.

4.1.4. Baseline Assessments

Baseline is defined as the last nonmissing measurement obtained before the first dose of epacadostat or pembrolizumab is administered.

4.1.5. Last Available Value

The last available value is the last nonmissing measurement obtained after starting epacadostat or pembrolizumab and within 90 days after the last dose of epacadostat or pembrolizumab.

4.1.6. Cycle Length and Duration

Cycle 1 Day 1 is defined as the day of the first dose of epacadostat or pembrolizumab. One treatment cycle consists of 21 days. The first cycle of therapy is defined as the period beginning with the first dose of epacadostat or pembrolizumab and ending the earlier of: (1) 21 calendar days (inclusive) later or (2) permanent discontinuation of epacadostat. Subsequent cycles have Day 1 as the corresponding visit date associated with the corresponding cycle.

4.2. Variable Definitions

4.2.1. Prior and Concomitant Medication

Prior medication is defined as any nonstudy drug started before the first dose of epacadostat or pembrolizumab.

Concomitant medication is defined as any nonstudy drug that is:

- Started before the date of first administration of epacadostat or pembrolizumab and is ongoing throughout the study or ends on/after the date of first study drug administration.
- Started on/after the date of first administration of epacadostat or pembrolizumab and is ongoing or ends during the course of study drug administration.

Note: A prior medication could also be classified as "both prior and concomitant medication" if the end date is on or after first dose of epacadostat or pembrolizumab. In the listing, it will be indicated whether a medication is prior-only, concomitant-only, or both prior and concomitant medication.

The start/stop dates recorded in the eCRF by the investigator and his or her research staff will be used to identify when a concomitant medication was taken during the study. Any missing start date must be queried for resolution. Unresolved missing start dates will be handled as follows:

- If the date is completely missing, the medication will be considered both prior and concomitant.
- If only the day is missing, and the last day of the month is before the first dose date on Day 1, then the concomitant medication will be considered as starting before Day 1, and the incomplete date will be imputed as the last day of the month.
- If only the day is missing, and the first day of the month is after the first dose date on Day 1, then the concomitant medication will be considered as starting after Day 1, and the incomplete date will be imputed as the first day of the month.
- If only the day is missing, and the month is equal to the month of the first dose date on Day 1, then the incomplete date will be imputed as the first day of the month.
- If both the month and day are missing, and the last day of the year is before the first dose date on Day 1, then the concomitant medication will be considered as starting before Day 1, and the incomplete date will be imputed as if it is the last day of the year. Otherwise, the incomplete date will be imputed as if it is the first day of the year.

5. STATISTICAL METHODOLOGY

5.1. General Methodology

Unless otherwise noted, SAS[®] software (SAS Institute Inc, Cary, NC; version 9.1 or later) will be used for the generation of all tables, graphs, and statistical analyses. Descriptive summaries for continuous variables will include, but not be limited to, the number of observations, mean, standard deviation, median, minimum, and maximum. Descriptive summaries for categorical variables will include the number and percentage of subjects in each category.

For the dose-escalation portion of the study, the safety evaluable population will be used for all safety analyses. For the cohort portion of the study, the safety evaluable population will be used for all safety analyses, and the efficacy evaluable population will be used for all efficacy analyses.

Interim analyses are planned for this study as defined in Section 9.

5.2. Treatment Groups

Subjects will be summarized overall and based on the dose regimen initially assigned:

- Pembrolizumab 2 mg/kg Q3W intravenously (IV) + epacadostat 25 mg BID
- Pembrolizumab 2 mg/kg Q3W IV + epacadostat 50 mg BID
- Pembrolizumab 2 mg/kg Q3W IV + epacadostat 100 mg BID
- Pembrolizumab 200 mg Q3W IV + epacadostat 300 mg BID
- Pembrolizumab 200 mg Q3W IV + epacadostat 50 mg BID (safety expansion)
- Pembrolizumab 200 mg Q3W IV + epacadostat 100 mg BID (safety expansion)
- Pembrolizumab 200 mg Q3W IV + epacadostat 300 mg BID (safety expansion)
- Pembrolizumab 200 mg Q3W IV + RP2D epacadostat (NSCLC PD-L1 high positive)
- Pembrolizumab 200 mg Q3W IV + RP2D epacadostat (NSCLC PD-L1 low/negative or indeterminate)
- Pembrolizumab 200 mg Q3W IV + RP2D epacadostat (Melanoma immune checkpoint-naive)
- Pembrolizumab 200 mg Q3W IV + RP2D epacadostat (Melanoma primary refractory)
- Pembrolizumab 200 mg Q3W IV + RP2D epacadostat (Melanoma relapsed)
- Pembrolizumab 200 mg Q3W IV + RP2D epacadostat (GU)
- Pembrolizumab 200 mg Q3W IV + RP2D epacadostat (TNBC)
- Pembrolizumab 200 mg Q3W IV + RP2D epacadostat (Ovarian cancer)
- Pembrolizumab 200 mg Q3W IV + RP2D epacadostat (SCCHN)
- Pembrolizumab 200 mg Q3W IV + RP2D epacadostat (DLBCL)
- Pembrolizumab 200 mg Q3W IV + RP2D epacadostat (RCC)
- Pembrolizumab 200 mg Q3W IV + RP2D epacadostat (MSI-high CRC)
- Pembrolizumab 200 mg Q3W IV + RP2D epacadostat (Gastric cancer)
- Pembrolizumab 200 mg Q3W IV + RP2D epacadostat (HCC)

Table summaries, unless otherwise indicated, will be provided by treatment group or tumor type.

5.3. Analysis Populations

5.3.1. Efficacy Evaluable Population

The efficacy evaluable population will include all subjects enrolled in the study who take at least 1 dose of study drug. This population will be used for analyses of all efficacy data.

5.3.2. Safety Evaluable Population

The safety evaluable population will include all subjects enrolled in the study who received at least 1 dose of study drug. Treatment groups for this population will be determined according to the actual treatment the subject receives on Day 1. All safety analyses will be conducted using the safety population.

6. BASELINE, EXPOSURE, AND DISPOSITION VARIABLES AND ANALYSES

Sample data displays are provided in Appendix E.

6.1. Baseline and Demographics, Physical Characteristics, and Disease History

The following demographic and baseline characteristics will be summarized for the safety evaluable population: age, sex, race, ethnicity, weight, height, ECOG performance status, staging, prior radiation (yes/no), prior surgery (yes/no), prior systemic therapy other than radiation (yes/no), and tumor-specific baseline disease characteristics (eg, BRAF mutation status [for melanoma] and human papillomavirus (HPV) status [SCCHN only]; refer to sample table shells for tumor specific details for each indication).

6.2. Disposition of Subjects

The number and percentage of subjects who were enrolled and who were withdrawn from treatment and from the study (with a primary reason for withdrawal) will be summarized for the safety evaluable population.

6.3. **Protocol Deviations**

Protocol deviations captured on the Protocol Deviation Log will be categorized, summarized, and presented in the subject data listings.

6.4. Exposure

For subjects in the safety evaluable population, descriptive statistics will be provided by cohort; duration of treatment; average daily dose (mg) of epacadostat; and number of cycles of pembrolizumab.

- **Duration of treatment:** The number of study days between Day 1 and the last nonzero dose administration record of epacadostat or pembrolizumab taken by the subject.
- **Number of cycles of pembrolizumab:** The number of cycles of pembrolizumab for a subject will be the number of administered, scheduled infusions of pembrolizumab recorded on the MK-3475 Dosing eCRF.

Subjects who stop pembrolizumab with SD or better may continue on monotherapy INCB024360 for up to 12 months or stop both therapies; if these subjects later experience disease progression, they may be eligible for up to 1 year of additional combination therapy followed by the option to continue monotherapy INCB024360 for up to 12 months as long as they are receiving benefit from treatment or they may stop both therapies.

NOTE: Protocol Amendment 10 removed the option for monotherapy epacadostat and re-treatment combination treatment for any subject who has not already started initiated such treatment.

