## 5. TREATMENT OF SUBJECTS

### 5.1. Administration of Study Drug

#### 5.1.1. INCB024360

**Note:** As of Amendment 10, INCB024360 administration is removed from the regimen for melanoma cohorts (except with medical monitor approval). Ongoing subjects with melanoma will be instructed to stop taking INCB024360 and to continue on MK-3475 alone (for up to the 35 infusions) or to stop treatment if on INCB024360 monotherapy unless medical monitor approval has been received to continue for the Protocol-specified interval (up to 12 months). Treatment with INCB024360 monotherapy and as part of combination therapy during the re-treatment periods is removed for subjects who have not already initiated such treatment. For those subjects who have already initiated INCB024360 monotherapy treatment or re-treatment and who do not have melanoma, treatment is limited to 12 months.

Subjects in Phase 1 will be administered study drug according to cohort enrollment ([Table 1](#)). Subjects in Phase 2 will be administered study drug at the dose or doses selected by the sponsor upon review of Phase 1 data.

All BID doses of INCB024360 will be taken orally morning and evening, approximately 12 hours apart without regard to food. If the morning or evening dose is missed by more than 4 hours, that dose should be skipped and the next scheduled dose should be taken at the usual time. Doses of INCB024360 will be self-administered except on the days scheduled to be given at the study clinic (see Section 7.8.1). INCB024360 will be given daily in combination with MK-3475 for approximately 24 months (35 administrations of MK-3475). After completion of 24 months of combination treatment, the option for treatment with INCB024360 monotherapy is available for up to 12 months for subjects who are receiving benefit from treatment and have not had disease progression or met any criteria for study withdrawal, or they may stop both INCB024360 and MK-3475. Monotherapy treatment is only available for subjects who have already initiated monotherapy at the time of implementation of Amendment 10. Medical monitor approval is required for monotherapy INCB024360 treatment beyond 12 months.

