Subjects who complete 24 months (35 administrations) of MK-3475, continue on monotherapy INCB024360 for up to 12 months or stop both therapies, and later experience disease progression may be considered for re-treatment with the combination for an additional 12 months (17 administrations of MK-3475) followed by the option to continue monotherapy INCB024360 for up to 12 months as long as they are receiving benefit from treatment and have not met any criteria for study withdrawal, or to stop both therapies. Intrasubject dose escalation of INCB024360 is not permitted.

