**Table 6: Dose Modification Guidelines for Drug-Related Adverse Events**

Toxicity	Grade	Hold Treatment (Y/N)	Timing for Treatment Restart	Dose/Schedule for Treatment Restart		Discontinue Subject (After Medical Monitor Consultation)
				INCB024360	MK-3475	
Hematologic toxicity	1, 2	No	N/A	N/A	N/A	N/A
	3	Yes	Toxicity resolves to $\leq$ Grade 1 or baseline	Restart at same dose	Restart at same dose and schedule. See Section 5.6.3 for recommendations regarding immune-mediated AEs.	Toxicity does not resolve within 12 weeks of last infusion.
	4	Yes	N/A	N/A	N/A	Permanently discontinue
Nonhematologic toxicity Note: Exception to be treated to similar Grade 1 toxicity: – Grade 2 alopecia – Grade 2 fatigue – Grade 3 rash in the absence of desquamation, no mucosal involvement, does not require systemic steroids, and resolves to Grade 1 within 14 days For additional information regarding AEs with potential immune etiology, see Section 5.6.3 or for subjects with HCC, refer to Appendix J for guidance related to hepatic adverse events.	1	No	N/A	N/A	N/A	N/A
	2	Consider holding for persistent symptoms	Toxicity resolves to $\leq$ Grade 1 or baseline	Restart at same dose	Restart at same dose and schedule. See Section 5.6.3 for recommendations regarding immune-mediated AEs.	Toxicity does not resolve within 12 weeks of last infusion
	3	Yes	Toxicity resolves to $\leq$ Grade 1 or baseline	Restart at 1 dose level lower.	Restart at same dose and schedule. See Section 5.6.3 for recommendations regarding immune-mediated AEs.	Toxicity does not resolve within 12 weeks of last infusion. Permanent discontinuation should be considered for any severe or life-threatening event.
	4	Yes	N/A	N/A	N/A	Permanently discontinue

Note: Subjects who experience a recurrence of the same severe or life-threatening AE at the same grade or greater with rechallenge of the combination should be discontinued from study treatment. For toxicities such as recurrent or intolerant rash with this combination, subjects may have the opportunity to resume treatment with MK-3475 alone with medical monitor approval.

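### SAP 6.4 defines a single treatment duration to the last dose of either drug: it counts the untreated interval before re-treatment and does not show time on each drug

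*SAP*

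**What the plan says.** SAP 6.4 plans three exposure statistics by cohort: duration of treatment, average daily dose of epacadostat, and number of pembrolizumab cycles. The duration is "The number of study days between Day 1 and the last nonzero dose administration record of epacadostat or pembrolizumab taken by the subject". Its starting point is set in SAP 4.1.1: "Day 1 is the date of first dose of epacadostat or pembrolizumab". Both ends of the span can therefore be set by either drug.

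The same section describes how dosing can stop and restart. Subjects who stop pembrolizumab with stable disease or better may go on to epacadostat alone "or stop both therapies; if these subjects later experience disease progression", "they may be eligible for up to 1 year of additional combination therapy". Protocol 5.1.1 sets re-treatment at 12 months, or 17 MK-3475 administrations.

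Time on one drug can arise in three ways:

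- **Melanoma, Amendment 10.** Protocol 5.1.1: "Ongoing subjects with melanoma will be instructed to stop taking INCB024360 and to continue on MK-3475 alone", up to infusion 35, with exceptions by medical monitor approval.
- **Toxicity.** The note to Protocol Table 6 says that for problems such as recurrent or intolerable rash, "subjects may have the opportunity to resume treatment with MK-3475 alone with medical monitor approval".
- **Epacadostat monotherapy.** Up to 12 months after 24 months of combination treatment. Since Amendment 10 this is open only to subjects who had already begun it.

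SAP 5.2 summarises subjects by the regimen first assigned, and every group listed is pembrolizumab plus epacadostat. The only exposure table in SAP Appendix E is Table 3.1.1, whose title names duration of exposure to both INCB024360 and MK-3475. Monotherapy and re-treatment dosing appear separately only in listings 2.5.3 to 2.5.5.

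**The concern.** A duration that ends at the last dose of either drug measures the span of a subject's dosing history, not time on treatment. The two agree when both drugs are given without a long break and stop together. They differ in the two situations this trial allows: a stop of both drugs followed by re-treatment, and a stop of one drug while the other continues. In the first, untreated days are reported as treated. In the second, the days are treated, but the summary does not say with what.

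The SAP's note on Amendment 10 in section 6.4 covers only the removal of monotherapy and re-treatment for subjects who had not started them. It does not mention that ongoing melanoma subjects were to come off epacadostat, so the definition was not adapted to that change.

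What is at stake is the descriptive exposure table. A reader who wants to know how long subjects took epacadostat, the investigational partner drug, cannot learn it from the statistics defined in 6.4.

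**Working it through.** The plan states no figure for this quantity, so there is nothing to reproduce. The check applies the SAP definition literally to illustrative subjects.

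**Inputs from the documents:** 21-day cycles; 35 MK-3475 infusions in the initial course; 17 in re-treatment; Day 1 is the first dose. **Assumptions:** infusions on schedule; epacadostat stopped with the final cycle of each course; the length of the gap; the cycle at which epacadostat stops in the one-drug case.

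**Initial course.** Infusion k falls on day 1 + 21(k − 1), so infusion 35 falls on day 1 + 34 × 21 = 715.

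**Re-treated subject.** Let g be the days from infusion 35 to the first re-treatment infusion.

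- SAP duration = 715 + g + 16 × 21 = 1051 + g.
- Off-drug days = g − 21, allowing one normal dosing interval after infusion 35.
- Duration without the off-drug days = 1051 + g − (g − 21) = 1072, whatever g is.

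| g (assumed) | SAP duration | Off-drug days | Overstatement |
|---|---|---|---|
| 90 | 1141 | 69 | 69/1072 = 6% |
| 180 | 1231 | 159 | 159/1072 = 15% |
| 365 | 1416 | 344 | 344/1072 = 32% |

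Protocol 6.2.1 also admits to re-treatment subjects who stopped after a confirmed complete response and at least 24 weeks of therapy. Their first course is shorter, so the same gap would be a larger share.

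**Epacadostat stopped, MK-3475 continued to infusion 35.** The SAP duration is 715 days in every case. Time on both drugs is 21 × (cycles with epacadostat).

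| Epacadostat cycles (assumed) | Days on both | Days on MK-3475 alone | Share of 715 |
|---|---|---|---|
| 8 | 168 | 547 | 77% |
| 17 | 357 | 358 | 50% |
| 26 | 546 | 169 | 24% |

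**Epacadostat monotherapy.** After 715 + 20 = 735 days of combination treatment, 365 days of monotherapy give a duration of 1100 days, of which 365/1100 = 33% is on epacadostat alone.

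**Whether another planned summary recovers this.** The pembrolizumab cycle count is a count of infusions given, so a gap does not inflate it, and it approximates time on that drug. For epacadostat there is only an average daily dose, and 6.4 states no denominator for it. If the single duration were used as the denominator (an assumption), a subject on 100 mg BID for 17 of 35 cycles would show 200 × 357/715 ≈ 100 mg per day while having taken 200 mg on each dosing day. Protocol 9.4.3 planned dose intensity by cycle and overall; SAP 6.4 does not carry it over. Listings 2.5.3 to 2.5.5 separate the records but leave the table unchanged, and none of them is specific to time on MK-3475 alone.

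**The case against.** The strongest reply is that the SAP calls the measure duration of treatment and says it runs to the last dose of either drug, so it does what it says. That is right on the label. A reader might infer from the combination group names and the title of Table 3.1.1 that the SAP presents this number as combination exposure; it never does. The reply does not rescue the re-treated subject, because days on neither drug are not treatment under any label.

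A reader might also infer that safety rates are distorted. The documents do not support this. Planned adverse event outputs in Protocol 9.4.3 and SAP 8.2 are counts and incidences of subjects. Nothing is divided by duration.

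Nor does the Protocol fix the length of an off-drug interval. Its 12-month limits apply to epacadostat monotherapy and to re-treatment. If the time between courses were spent on monotherapy, there would be no untreated gap.

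Timing limits the larger illustrations. Re-treatment survives only for subjects who had begun it by Amendment 10 (2 July 2018). The Phase 2 cohorts entered the Protocol in Amendment 4 (20 May 2015) and the 100 mg BID dose in Amendment 5 (11 January 2016). Twenty-four months from those dates leaves about 13 months or under 6 months before Amendment 10. Likewise, SAP Amendment 4 (17 May 2019) came 319 days after Protocol Amendment 10. Of the melanoma illustrations (547, 358 and 169 days on MK-3475 alone), only the last could have run in full by that date if the switch came with the amendment. The data cutoff is not given.

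Finally, Table 3.1.1 is marked as a standard table, and its shell is not in the documents. It may contain rows per drug. If so, the derivation behind those rows is still missing from 6.4, which is where the SAP defines exposure.

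**Conclusion.** The point stands as a minor one. Followed exactly, SAP 6.4 counts untreated days as treatment for re-treated subjects who had stopped both drugs, and defines no time on each drug for subjects who continued on only one. The illustrated overstatement is 6% to 32% for assumed intervals of 90 to 365 days. The illustrated share on MK-3475 alone is 24% to 77% of a 715-day duration. These are per-subject examples, not estimates for the trial.

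The effect is confined to descriptive exposure. The objective response rate test, adverse event incidences and the interim safety rule do not use this duration. A reader might take the Amendment 10 switch to mean that the problem is widespread. The documents do not show that: they give no count of affected subjects, the switch reached only melanoma subjects still on treatment, with exceptions, and Protocol 5.4 expects participation to average about 6 months. Re-treatment is narrower still. The number affected is unknown and probably small.

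**What to change.** In SAP 6.4, replace the single definition with:

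1. duration of epacadostat and duration of pembrolizumab in the initial course, each from its own first to its own last nonzero dose;
2. re-treatment summarised as a separate course, with the same two durations;
3. a statement that the off-drug interval between courses is excluded.

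It would help to state whether epacadostat monotherapy belongs to the initial course, and to give the denominator for average daily dose. Table 3.1.1 can keep its title, which would then match its content.

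The cost is a minor derivation change with no new data. Dosing records for each drug already feed listings 2.5.1 to 2.5.5, and SAP 6.5 already uses permanent discontinuation of epacadostat as an end point for intended dose, so a drug-specific window is not new to the plan.
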